11.2 Definition of endpoints

11.2.1 Incidence of adverse events

Regarding AEs occurring during the protocol treatment, the incidence of each AE of the worst grade according to the CTCAE v4.03 throughout the entire cycles will be calculated.

11.2.2 Objective response rate (ORR)

ORR is defined as the proportion of patients whose best overall response, as per the RECIST guideline version 1.1 and irRECIST, is either CR or PR.

11.2.3 Progression-free survival (PFS)

PFS is defined as the time from the enrollment date to either the date when disease progression is determined or the date of death from any cause, whichever came earlier.

- "Progression" is defined as PD in the assessment of overall response by diagnostic imaging based on the RECIST guideline version 1.1, and the imaging examination date is set as the date of progression. For clinical PD, the date when clinical PD is documented is defined as the date of progression.
- Surviving patients who are not assessed as having progression will be censored on the last date on which an absence of clinical progression is confirmed (hereinafter referred to as the "last date of progression-free survival confirmed). (If information on progression or progression-free is obtained from a medical institution to which the patient was transferred or referred, a patient referral document indicating the basis for the diagnosis should be received and retained. Obtaining the information by telephone only is not permitted.)
- Patients who died without being assessed as progression are handled as having "an event occurring on the date of death" in principle, unless the period from the last confirmation date of progression-free survival to the date of death is long.

Whether to handle the patient as being "censored on the last confirmation date of progression-free survival" should be determined in the case review meeting to be held as required, before the data are finalized.

- Patients with treatment discontinuation for reasons such as AEs and their refusal to continue participation, who are given another treatment as subsequent treatment, should be handled as being "censored on the start date of the subsequent treatment."
- The occurrence of a secondary malignancy (metachronous multiple cancers) will not be considered either an event or censoring, but will be considered PFS until another event is observed.

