The trial will proceed as follows for all subjects. After providing written informed consent to participate in the trial, each subject will undergo preliminary examination in the preceding 2 weeks (day -14 to -1) before receiving the investigational drug. Subjects who are enrolled in the trial will be admitted to the hospital the day that the administration of the investigational drug begins (cycle 1, day 1), and they will receive the investigational drug at the appropriate dose for each level. After completing the prescribed observations and tests on cycle 1 day 4, the subjects are allowed to be discharged. Furthermore, the subjects will be administered the investigational drug and undergo the prescribed tests on cycle 1 day 8, cycle 1 day 15, cycle 1 day 22, cycle 2 day 1, and cycle 2 day 15, after which they will undergo the test once every 2 weeks until the criteria for termination are satisfied. After treatment is discontinued, the subjects will undergo follow-up tests on days 30 after the final day of treatment. Thereafter, the survival of each subject will be investigated every 90 days.

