8.5 Tumor evaluation

For all subjects, tumor evaluations will be conducted using the irRECIST and RECIST guidelines version 1.1. Tumor evaluations of the chest, abdomen, and pelvis (when deemed clinically necessary) will be conducted at each time point listed below until an exacerbation is

confirmed. Thoracoabdominal and pelvic contrast-enhanced CT or MRI will be performed (if the subject is allergic to the contrast medium, plain scans are permitted).

- Less than 21 days before enrollment in this trial
 - Evaluations will be performed in weeks 6, 12, 18, and 24 after the beginning of treatment (followed by every 9 weeks until week 42, then every 12 weeks thereafter).
- When treatment is terminated for reasons other than an exacerbation of the underlying disease on imaging, an evaluation will be performed within 2 weeks of dosing completion. Furthermore, tumor evaluations are to be conducted in accordance with the schedule until an exacerbation of the underlying disease is confirmed, or until commencement of a new anticancer treatment.

The principal investigator and radiologist will conduct tumor evaluations in accordance with the irRECIST and RECIST guidelines version 1.1 (refer to appendices 2 and 3). The decision to continue the investigational drugs will be determined on the basis of these evaluations, including the effects on target and nontarget lesions and the appearance of new lesions. When disease progression is first observed on imaging in clinically stable patients, participating medical institutions will conduct repeat scans 4 weeks after the initial identification of disease progression via an image evaluation to determine disease progression. Administration of the investigational drug can continue until the repeat scan is conducted (refer to Table 10). The criteria for clinical stability are listed below.

- Absence of clinical signs and symptoms indicating disease progression.
- No worsening of ECOG PS.
- No sudden disease progression observed

• Absence of tumor enlargement in the main anatomical site requiring new emergency medical intervention (e.g., spinal cord compression).

Furthermore, in the present trial, a maximum of 10 lesions can be included as target lesions, with a maximum of five lesions per organ.

| Table 8.5: Imaging and investigational drug dosing after disease progression is first observed |
|--|
| on imaging |

| | Clinically stable | | | | Clinically unstable | | | |

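### PFS censoring in 11.2.3 follows the last clinical date with no limit on time since the last scan, which can modestly overstate PFS; 12.7.2 needs a last-scan sensitivity analysis

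*Combined protocol and SAP*

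**What the plan says.** Section 11.2.3 has two kinds of progression event besides death:

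- Radiographic progression "is defined as PD in the assessment of overall response by diagnostic imaging based on the RECIST guideline version 1.1". It is dated by the scan that shows it: "the imaging examination date is set as the date of progression".
- Clinical progression has its own date: "For clinical PD, the date when clinical PD is documented is defined as the date of progression".

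It has two censoring rules that matter here:

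- Survivors not assessed as having progressed are "censored on the last date on which an absence of clinical progression is confirmed". No scan is required on or near that date. Information from another hospital is accepted if a referral document gives the basis for the diagnosis; a telephone call alone is not enough.
- Patients who stop treatment for reasons such as adverse events or refusal and then receive another treatment are "censored on the start date of the subsequent treatment", not at the last scan before it.

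The scan schedule in 8.5 opens with 6-week gaps: "Evaluations will be performed in weeks 6, 12, 18, and 24 after the beginning of treatment". The gaps then widen: "followed by every 9 weeks until week 42, then every 12 weeks thereafter". Clinical contact is more frequent. Section 2.8 lists the early visits, "after which they will undergo the test once every 2 weeks until the criteria for termination are satisfied".

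Section 8.5 asks for scans to continue on schedule after treatment stops without imaging progression, until progression or a new anticancer treatment. Section 6.2.2 lets the attending physician omit tests after termination. Section 12.7.2 plans Kaplan-Meier estimates with medians and annual rates. It has no missed-scan rule and no alternative censoring rule.

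**The concern.** A patient who is seen but not scanned stays in the Kaplan-Meier risk set, although radiographic progression cannot be recorded for that patient. If clinical visits miss some of the progressions that a scan would have shown, the observed event rate in that stretch is too low and the PFS curve is too high.

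The plan leaves room for such stretches. The clinical date will usually fall after the last scan, tests may be omitted after termination, and outcome follow-up under 8.7 runs to two years after the last enrollment.

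The trial is single-arm, so no control group shares the error and cancels it. Section 12.5 makes the secondary endpoints part of judging whether the combination merits further development. No error rate or sample size depends on PFS.

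**Working it through.** The plan states no PFS assumption, event count or power, so there is no figure of its own to reproduce. The check is of the rule itself.

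**Step 1. Scan gaps.** From 8.5, scans fall at weeks 6, 12, 18 and 24, then 24 + 9 = 33 and 33 + 9 = 42, then 42 + 12 = 54 and so on. If every scan is done, the unscanned stretch before censoring is at most about 6, 9 or 12 weeks, apart from visit windows. If scans stop, 11.2.3 sets no limit.

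**Step 2. All scheduled scans done.** Assumed inputs: exponential progression with a median of 8, 13 or 26 weeks; 10-30% lost to follow-up; visits every 2 weeks; 30% of progressions also detectable clinically; 400,000 simulated patients per setting. The plan's rule came within about 0.3 points of the true progression-free proportion at weeks 24 and 42. Example, median 13 weeks and 20% lost, week 24:

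- truth: 0.5^(24/13) = 0.278
- plan's rule: 0.276
- last-scan censoring: 0.273

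The reason is that a patient censored between two scans is at risk at the first and gone by the second under either rule, so scan-detected events see almost the same denominators.

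**Step 3. Imaging stops early while visits continue.** Same model, with 20-30% lost, imaging ending early in 10-30%, and clinical detection of 30% (0% in some settings).

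| | Plan's rule above truth | Part removed by last-scan censoring |
|---|---|---|
| Week 24 | 1.0-4.4 points | 0.5-2.1 points |
| Week 42 | 1.3-5.2 points | 0.4-3.3 points |

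Example, median 13 weeks, 20% lost, 20% stopping imaging, week 24: 0.307 (plan), 0.296 (last scan), 0.278 (truth). The plan overstates by 0.307 - 0.278 = 2.9 points, of which 0.307 - 0.296 = 1.1 are removed. The rest comes from progression found late or never, which no censoring date repairs. The median differed between the rules by at most 0.7 week.

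**Step 4. Dependence on clinical detection.** Assumed inputs: true median PFS of 3, 5 or 8 months; the scan schedule in 8.5; 20% or 40% of patients given an exponential time to leaving scans with mean equal to the median, so that 13-28% leave before progression is seen; then 1-3 months of clinical follow-up only. The figures are errors in 6-month PFS against complete scanning. Where two runs differed in the last digit, the wider range is shown.

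| Share of progressions in the gap detected clinically | Plan's rule | Last-scan censoring, clinical events still counted |
|---|---|---|
| 0% | +1.1 to +6.6 | about 0 |
| 30% | +0.7 to +4.2 | -0.4 to -1.5 |
| 60% | +0.3 to +1.9 | -0.7 to -2.9 |
| 100% | -0.2 to -0.9 | -1.2 to -4.5 |

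These move by a few tenths of a point with the date given to a clinically detected progression.

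**Step 5. Scale.** With 30 patients and a 6-month PFS of 0.28, the binomial standard error is sqrt(0.28 × 0.72 / 30) = 0.082, or about 8 points.

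**The case against.** The strongest defence is that the rule is coherent. Clinical progression is an event with its own date, so clinical follow-up yields events as well as censoring, and a clinical censoring date matches that half of the definition. The plan also tries to limit unscanned time: 8.5 requires a scan within 2 weeks of stopping for non-imaging reasons, scheduled scans thereafter, and an effort to confirm clinical progression by imaging even after termination. PFS is secondary, 12.5 calls the study exploratory, and 12.7 allows listings alone.

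Much of this stands, and it rules out two stronger readings.

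- A reader might infer that PFS is biased upward, and in one direction only. The documents do not support that. The bias needs missed or stopped scans together with missed clinical progression. It is negligible in Step 2 and slightly negative at full detection in Step 4.
- A reader might infer that last-scan censoring should replace the primary rule. While clinical progression remains an event, that rule counts clinical events after the last scan but discards clinically progression-free time after it. That is why it falls 0.4-4.5 points low once any progression is detected clinically.

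What the defence does not answer is that 6.2.2 permits omitted tests, 11.2.3 sets no limit on the gap, and 12.7.2 gives no way to see whether the choice mattered.

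**Conclusion.** The point holds as a modest and conditional one. When clinical follow-up outlasts imaging and clinical visits miss some progression, the rule in 11.2.3 can overstate 6-month PFS by about 0.3-6.6 points, assuming that 13-28% leave scans early and that 0-60% of their progressions are detected clinically. The upper end needs a 3-month median, the highest drop-out and no clinical detection at all. With scheduled scans done, the effect is negligible. In all these settings it is smaller than the standard error of about 8 points with 30 patients, although a larger sample would not remove it.

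None of the drop-out, detection or median figures comes from the documents. In Step 4 the two rules bracketed the complete-scan value at 30% and 60% detection. At full detection both lay below it, and in the Step 3 example both lay above the truth, so the bracket is approximate. A planned sensitivity analysis is a cheap improvement; changing the primary definition is not warranted.

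**What to change.** Keep the clinical-date rule in 11.2.3 as primary. Add one planned sensitivity analysis of PFS to 12.7.2:

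1. Censor patients without progression at their last evaluable RECIST 1.1 assessment, or at the enrollment date if there is none.
2. Apply the same rule to patients whom 11.2.3 censors at the start of subsequent treatment.
3. State in advance how clinical progression documented after the last scan is handled. Counting it as an event while discarding clinically progression-free time biases PFS downward, so the choice must be visible.
4. Report both results side by side and read them as an approximate bracket.

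Scan dates are already collected under 8.5. The cost is a few sentences in 12.7.2, a little more analysis work, and a second PFS figure that will be slightly less favourable.

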11.2.4 Disease control rate (DCR)

DCR is defined as the proportion of patients whose best overall response assessed based on the RECIST guideline version 1.1 and irRECIST is any of CR, PR, or SD.

11.2.5 Overall survival (OS)

OS is defined as the period from the date of enrollment to the date of death from any cause.

Surviving patients will be censored on the last confirmation date of survival (confirmation of survival by telephone is permitted; however, the fact that survival is confirmed should be recorded in the medical record, etc.).

Patients lost to follow-up will be censored on the last date on which their survival has been confirmed before being lost to follow-up.

12 Statistical Matters

This protocol stipulates the statistical analysis plan. If any change arises in the statistical analysis plan, it should be described in the clinical study report, including its background. A summary of the statistical analysis plan is described below.

12.1 Handling of patients

The handling of patients will be determined by the representative coordinating investigator after discussing with the data center.

12.2 All enrolled patients

"All enrolled patients" are defined as patients enrolled in this study in accordance with Section "5.

Enrollment," excluding those who have been enrolled multiple times or mistakenly enrolled.

| 10 0 | D | • . • | e | | | |
|------|-------|-------|-------|---------|-------|---------|
| 12.5 | Defin | ition | of an | 9 VCIC | nonii | lations |
| 14.0 | Dum | nuon | or an | ary 515 | popu | autons |

Each analysis population is defined below.

| Abbreviation | Analysis population | Definition |
|--------------|---------------------|---|
| None | DLT analysis set | See Section "6. Treatment Regimen and |
| | | Treatment Modification Criteria." |
| SP | Safety population | The population of patients who received |
| | | the investigational product at least once |
| | | among all enrolled patients. |
| FAS | Full analysis set | The population of patients that excludes |
| | | those to whom the following applies |
| | | from all enrolled patients: |
| | | • Patients who should have been judged |
| | | as clearly ineligible based on the |
| | | information before enrollment |
| | | (ineligible patients). |

12.4 Data handling

The handling of data (e.g., inclusion or exclusion criteria for the analysis population) will be determined by the coordinating committee after discussing with the data center.

12.4.1 Handling of missing values and outliers

In principle, imputation of missing values and analyses dealing with outliers will not be performed. However, when the presence of missing values or outliers that may have a significant impact on analysis results is identified before data lock, the handling of such data will be determined at a case review meeting and the measures to be taken will be described in the case review meeting minutes.

12.4.2 Dealing with additional analyses

All analyses planned in this study are specified in Section "12.5 Positioning of analyses and analysis methods." Analyses other than the final analysis are regarded as additional analyses. The results from additional analyses will be reported with a note clarifying that the analyses were not planned in advance, or will be reported in a separately prepared additional analysis report.

12.5 Positioning of analyses and analysis methods

As the purpose of this study is exploratory examination, future decision-making rules will not be specified. However, if this study allows the dose finding for the investigational products, demonstrates a certain level of safety, and confirms the efficacy and safety of the protocol treatment in other secondary endpoints, the future development of the protocol treatment of this study will be regarded as promising. In this study, the following one-time analysis (final analysis) will be performed. The advisability of the dose-level transition will be decided by the coordinating committee. However, since the decision on transition is made only based on the evaluation of the incidence of DLTs, analyses related to dose-level transition are positioned as part of monitoring.

12.6 Safety analysis

12.6.1 Analysis of the incidence of AEs

The occurrences of AEs in the SP will be summarized. Confidence intervals will not be constructed, and subgroup analysis will not be performed.

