2.8.1 Setting of endpoints Primary endpoints

In patients with unresectable recurrent solid tumors who are refractory or intolerant to standard chemotherapy, the safety and tolerability of a repeated dose of regorafenib and nivolumab will be evaluated, and the MTD and RD of the two drugs when used in combination will be examined.

Dose-escalation cohort

In patients with unresectable recurrent solid tumors who are refractory or intolerant to standard

chemotherapy, the safety of regorafenib and nivolumab combination therapy will be evaluated to determine the MTD and RD of regorafenib according to DLT when used in combination.

Expansion cohort

An exploratory evaluation of the efficacy and safety of the combination therapy will be performed on the basis of the RD found in the dose-escalation cohort.

Secondary endpoints

• Safety

- According to the NCI- CTCAE version 4.0, the incidence and type of adverse events that occur during treatment will be evaluated.

- Efficacy
 - ORR according to RECIST ver. 1.1, and irRECIST
 - PFS
 - OS
- DCR

Exploratory items (performed as accompanying research in the present trial):

Tests of various biomarkers

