6.1.4 Target subjects for DLT evaluation

For each level, at least three subjects will be enrolled, and the presence or absence of DLT will be evaluated during the DLT evaluation period.

When it is determined that there is a subject who will not change levels, an additional subject will

be enrolled to evaluate the DLT determined in 6.1.3.

Furthermore, among the enrolled subjects, those who meet the following conditions will be excluded from DLT evaluation:

1) Subjects who are unable to receive regorafenib for ≥ 14 days in the first course for reasons other than toxicity.

2) Subjects for whom sufficient data cannot be obtained to determine the DLT evaluation because of missing mandatory tests, etc.

3) Cases in which adequate data for DLT evaluation judgment could not be obtained due to essential test defects

Furthermore, among the participants who withdraw from regorafenib and nivolumab during the first course for reasons other than adverse events or who withdraw from treatment for a long period because of toxicities other than DLT, the decision to subject such patients to a DLT evaluation will be determined upon deliberation between the trial coordinating committee and the participating institution.

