12.12 Special notes on analysis items

12.12.1 Items summarized and analyzed in the final analysis

In the final analysis, the following items will be analyzed.

<Items to be summarized>

- Demographic data
- Concomitant therapies
- Changes in laboratory values

To summarize a continuous variable, general descriptive statistics (mean, median, minimum, maximum, etc.) will be calculated.

<Items to be analyzed>

- Incidence of AEs
- Objective response rate (ORR)
- Disease control rate (DCR)
- Progression-free survival (PFS)
- Overall survival (OS)

<Subgroup analysis to be performed>

Subgroup analyses will be performed in an exploratory manner for the following factors. In these

analyses, adequate statistical power is not guaranteed and adjustment for multiplicity is not performed. Therefore, the results of each subgroup analysis will be interpreted as exploratory results.

- Cancer type
- Presence or absence of anti-PD-1 antibody use in the prior treatment

Since data on the following factors will be collected in an additional study to this study, the following subgroup analysis results will not be included in the clinical study report of this study.

- PD-L1 (Negative / Positive)
- MMR (Proficient / Deficient)
- TMB (High / Low)

etc.

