12.12.2 Analysis items included in the clinical study report

The following analysis items will be included in the clinical study report.

<Efficacy evaluation (Analysis population: all enrolled patients)>

- Demographic data
- Objective response rate (ORR)
- Disease control rate (DCR)
- Progression-free survival (PFS)
- Overall survival (OS)

<Safety evaluation (Analysis population: SP)>

- Incidences of DLTs/AEs (number of patients with DLTs/AEs and the incidence, by the worst grade)
- Summary statistics of laboratory values and their changes

<Tables, figures and graphs referred to but not included in the text of the clinical study report>

- Listings of deaths, other serious and significant adverse events
- Laboratory value listing by patient

<Appendix>

- List of discontinued patients
- List of patients with serious protocol deviations
- List of patients excluded from FAS
- History of prior treatment
- List of concomitant medications and therapies
- Compliance
- List of efficacy response data by patient (tumor assessment, OS, PFS, subsequent treatment, and tumor markers)
- Adverse event listing by patient

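### Section 12.12.2 reports DLT incidence in the safety population rather than the DLT analysis set, and no AE or efficacy estimate at the recommended dose is specified

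*Combined protocol and SAP*

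**What the plan says.** - **Objective.** For the expansion cohort, Section 2.8.1 says that an exploratory assessment of "efficacy and safety of the combination therapy will be performed on the basis of the RD found in the dose-escalation cohort".
- **AEs.** Section 12.6.1: "The occurrences of AEs in the SP will be summarized. Confidence intervals will not be constructed, and subgroup analysis will not be performed". The SP (Section 12.3) is every enrolled patient dosed at least once, so it covers all dose levels and both cohorts.
- **DLTs.** Section 12.3 defines a "DLT analysis set" by reference to Section 6, and Section 6.1.4 says that among enrolled subjects "those who meet the following conditions will be excluded from DLT evaluation". Section 12.12.2, however, lists under its SP heading "Incidences of DLTs/AEs (number of patients with DLTs/AEs and the incidence, by the worst grade".
- **Efficacy.** The heading in Section 12.12.2 over ORR, DCR, PFS and OS is "<Efficacy evaluation (Analysis population: all enrolled patients)>".
- **Subgroups.** Section 12.12.1 plans two for the study report: cancer type, and "Presence or absence of anti-PD-1 antibody use in the prior treatment". Dose level and cohort are not among them.
- **Unplanned analyses.** Under Section 12.4.2, results outside the final analysis are to be "reported with a note clarifying that the analyses were not planned in advance" or placed in a separate report.

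**The concern.** A phase I report has to tell the reader how toxic and how active the regimen is at the dose taken forward. The populations that Section 12.12.2 names do not give that figure.

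For DLTs there is an internal mismatch. One section defines a set for the purpose, and another assigns the result to a larger set. That larger set contains expansion patients, who enter after the escalation DLT evaluation has finished (Section 6.1.5), and any treated escalation patients whom Section 6.1.4 removes. Neither group can contribute to the numerator in the intended way, so the rate is diluted.

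For AEs and efficacy, the named populations pool patients at the RD with patients at other doses, and neither planned subgroup factor separates them. Cancer type is no proxy for cohort: escalation admits any solid tumour (Section 4.1), including the three expansion types. Section 12.5 would call further development promising on the strength of these safety and efficacy results.

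**Working it through.** **1. Planned sizes.** Section 2.8.2 gives 3 to 6 patients at each of three levels, 9 to 18 in total: 3 × 3 = 9 and 3 × 6 = 18, which reproduces. Section 12.8 gives 12 to 18. The lower figure does not follow from 3 × 3, but it does from 3 + 3 + 6, that is, if level 3 needs six patients. Adding about 30 expansion patients gives an SP of 39 to 48 if all are dosed. Expansion patients are then 30/48 = 62.5% to 30/39 = 76.9% of it.

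**2. DLT denominator.** The counts below are assumed examples. All patients are taken as treated and evaluable, with 30 in expansion and no DLT assigned there.

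| DLTs at levels 1, 2, 3 | RD | At the RD | DLT analysis set, all levels | SP |
|---|---|---|---|---|
| 0/3, 0/3, 1/6 | level 3 | 1/6 = 16.7% | 1/12 = 8.3% | 1/42 = 2.4% |
| 1/6, 1/6, 2/6 | level 2 | 1/6 = 16.7% | 4/18 = 22.2% | 4/48 = 8.3% |

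The fourth column shows that the right set still needs splitting by level.

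**3. Share of pooled patients not at the RD.** Inputs from Sections 6.1.2 and 6.1.4:

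- each opened level enrols at least three;
- a level passes at 0/3 or 1/6;
- a failing level holds 3 to 6;
- the RD level holds 6, or 3 if level 3 may clear at 0/3.

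With E expansion patients, share = off-RD patients ÷ (escalation patients + E).

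| Escalation path | E = 30 | E = 40 | E = 60 |
|---|---|---|---|
| Lowest: 6 + 3 + 0, RD level 1 | 3/39 = 7.7% | 3/49 = 6.1% | 3/69 = 4.3% |
| Highest: 6 + 6 + 3, RD level 3 | 12/45 = 26.7% | 12/55 = 21.8% | 12/75 = 16.0% |

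If level 3 needs six patients, the highest share at E = 30 is 12/48 = 25.0%. E = 40 reflects the roughly 10 patients that Section 2.8.2 may add for one cancer type, and E = 60 the same for all three types (30 + 3 × 10).

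**4. Effect on a rate.** Pooled rate − RD rate = share × (off-RD rate − RD rate). For a 10-point difference and E = 30, this is 0.077 × 10 ≈ 0.8 points to 0.267 × 10 ≈ 2.7 points. It is zero if the rates are equal. The documents give no rates by dose for the combination, so no single shift can be stated.

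**The case against.** The best defence is that an analysis population fixes who is counted, not which columns a table has. Section 12.6.1 does not say that AEs are shown only in one pooled column. Section 2.8.1 lists the RD evaluation under primary endpoints, and Section 12.11 says that all endpoints are analysed, so an RD display may already belong to the final analysis. The DLT analysis set has no evident use except DLT incidence, so the SP heading looks like a slip. At least 33/45 = 73.3% of pooled patients are at the RD. Section 12.5 sets no decision rules, Section 12.7 allows efficacy to be shown as listings only, and by-patient listings are planned.

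Much of this stands, and it rules out several stronger readings:

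- **Dose-level tables are forbidden.** A reader might infer this from the ban on AE subgroup analysis. The text does not say so.
- **The MTD or RD could be chosen wrongly.** It could not for this reason: Section 6.1.2 counts DLTs level by level.
- **An RD table must carry the unplanned label.** Section 12.4.2 makes that possible, but Section 12.11 makes it uncertain.
- **A level may close after two patients**, which would give 2/38 = 5.3%. Item 3 of Section 6.1.2 might suggest it, but that section registers three before evaluation and Section 6.1.4 requires at least three.

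What the defence does not supply is a sentence that puts DLT incidence on its own set, or one that specifies an RD estimate. Section 12.11 says that endpoints are analysed; Section 12.12.2 says in whom. Listings are not a planned estimate.

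**Conclusion.** The point holds in two parts of unequal strength.

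The DLT denominator in Section 12.12.2 is wrong as written, because it conflicts with Sections 12.3 and 6.1.4. Taken literally, the error is large: 16.7% at the RD is reported as 2.4% in the first example. That size assumes that all expansion patients count in the denominator and that none is assigned a DLT.

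The missing RD estimate is a gap in specification rather than an error. Its effect is modest: at E = 30, about 0.8 to 2.7 points per 10-point difference between off-RD and RD rates, less if expansion is enlarged, and none if the rates agree. This assumes patients are counted at their assigned level and that all enrolled patients are treated.

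Both parts concern the final report only, and both should be corrected before the final analysis.

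**What to change.** Suggested wording:

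- **Section 12.12.2, safety:** *DLT incidence will be reported by dose level in the DLT analysis set.*
- **Section 12.6.1:** *AE incidence by worst grade will be tabulated by assigned dose level, for all patients treated at the RD, and for the SP overall.*
- **Section 12.12.2, efficacy:** *ORR, DCR, PFS and OS will be reported for the expansion cohort and for all RD-treated patients, alongside all enrolled patients.* Add a note that RD-treated escalation patients may have tumour types other than the three in expansion, so that group is itself mixed.

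The pooled totals can stay; closing the gap does not require demoting them. The cost is extra table columns and one changed denominator, from data already collected. RD figures will have smaller denominators, and so wider intervals where intervals are given, than the pooled ones.
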